5.3 Procedures for handling subjects incorrectly randomized

Volunteers who fail to meet the inclusion/exclusion criteria should not, under any circumstances, be randomized into the study. There can be no exceptions to this rule.

Where a subject, who does not meet the selection criteria, is randomised in error and this is identified before dosing, the subject should be withdrawn from the study. A discussion should occur between the CPA Physician and the Investigator regarding whether a replacement may be considered. The CPA Physician is to ensure all such decisions are appropriately documented.

Where subjects are enrolled but subsequently fail to meet the study criteria post initiation, a discussion should occur between the CPA Physician and the Investigator regarding whether to continue or discontinue the subject from treatment.

If a subject is withdrawn from study drug they should be advised to continue assessments for safety monitoring.

The CPA Physician is to ensure all such decisions are appropriately documented. In situations where an agreement cannot be reached, the volunteer should have their study therapy stopped.

5.4.2 Methods for unblinding the study

Individual treatment codes, indicating the treatment randomization for each randomized volunteer, will be available to the Investigator or pharmacist at the study center.

The treatment code should not be broken except in medical emergencies when the appropriate management of the volunteer requires knowledge of the treatment randomization. The Investigator documents and reports the action to the Sponsors, without revealing the treatment given to the volunteer to the Sponsors' staff. Following completion of Part A, an unblinded review of the ISR incidence will be performed, as described in Section 5.8.

The Sponsors retain the right to break the code for SAEs that are unexpected and are suspected to be causally related to an IP and that potentially require expedited reporting to regulatory authorities. Treatment codes will not be broken for the planned analyses of data (other than as described in Section 5.8) until all decisions on the evaluability of the data from each individual volunteer have been made and documented.

5.5 Treatments

5.5.1 Identity of investigational product(s)

Investigational product	Dosage form and strength	Manufacturer
Ceftaroline fosamil	600 mg of ceftaroline fosamil a pale yellowish-white to light yellow crystalline powder in a single-dose, clear glass 20 mL vial	

The formulation number and batch numbers will be recorded in the Study Master File and identified in the CSR.

Ceftaroline fosamil for infusion is supplied as 600 mg of ceftaroline fosamil (the prodrug of ceftaroline), a sterile pale yellowish-white to light yellow crystalline powder in a single-dose, clear glass 20-mL vial. An excipient, L-arginine (approximately 660 mg L-arginine/g of prodrug) is added as an alkalizing agent to maintain the pH of the constituted solution to pH 4.8 to 6.2. The investigational site will be responsible for diluting the concentrate to obtain the desired infusion volume.

Placebo for Part A will consist of 0.9% sodium chloride infusion fluid of various infusion volumes (ie, 50, 100, or 250 mL) as appropriate.

The constitution time should be no more than 120 seconds. After constitution of ceftaroline fosamil vials, infusion solution preparation must be completed within 30 minutes. The diluted iv solutions should be administered promptly, however the drug product has been shown to be physically and chemically stable for 6 hours at 23°C to 25°C, or for 24 hours at 2°C to 8°C, followed by 6 hours at 23°C to 25°C. Therefore, once the constituted vial is diluted in the infusion bag or bottle, it should be administered within 6 hours of the initial constitution, or refrigerated for 24 hours at 2°C to 8°C, then administered within 6 hours when stored below 25°C.

Reconstituted solutions and subsequent infusions should be prepared using standard aseptic techniques.

Those individuals involved in the drug-dispensing procedure should also be aware that ceftaroline fosamil is a cephalosporin-type drug, which carries some safety concerns and should not be handled by staff members with known allergies to this type of product.

Product preparation requirements

The following will be used to administer study drug:

Ceftaroline:

- Ceftaroline fosamil powder 600 mg containing L-arginine alkalizing agent

- Sterile water for infusion, USP
- 0.9% sodium chloride infusion fluid (50, 100, or 250 mL infusion bags, as appropriate)
- Standard catheters approved for use in both the US and EU

Placebo for Part A will consist of 0.9% sodium chloride infusion fluid (50, 100, or 250 mL infusion bags).

See Table 5 for the constitution of the ceftaroline fosamil and volume to be inserted into infusion bag. The extractable volume of the reconstituted vial should then be transferred to the 0.9% sodium chloride infusion bag to achieve the final bag volume.

Table 5 Concentration and extractable volumes of reconstituted active drug

Active drug	Volume of water required for reconstitution of vial	Extractable volume of reconstituted vial	Solution concentration
Ceftaroline fosamil 600 mg	20.0 mL	20.7 mL	29 mg/mL

Further instructions regarding dose preparation, blinding, and administration will be documented in separate pharmacy handling instructions.

5.5.2 Doses and treatment regimens

During Part A, each volunteer will receive simultaneous bilateral iv infusions of IP (ceftaroline fosamil 600 mg in 1 arm and placebo in the other arm) over 60 minutes every 12 hours for a maximum of 72 hours (6 infusions). Volunteers will then enter a minimum 4.5-day (approximately 108 hours) washout period before crossing over and receiving simultaneous bilateral iv infusions of IP (ceftaroline fosamil 600 mg in the contralateral arm from Period 1 and placebo in the other arm), in veins different than those used previously, over 60 minutes every 12 hours for a maximum of 72 hours (6 infusions). Should the volunteer experience an ISR of 2 or greater as measured by the Visual Infusion Phlebitis (VIP) scale (see [Appendix D](#)), the infusion must be stopped on that arm (ie, the cannula will not be resited for that treatment period) and the ISR will be recorded as an AE. The infusion on the other arm will continue, as appropriate. See Section [5.8](#) for study stopping criteria and Section [3.1.1](#) for a description of treatments and treatment sequences.

In Part B, each volunteer will receive a single dose of 600 mg ceftaroline fosamil infused over 60 minutes in each crossover period (Days 1 and 3). See Section [3.1.2](#) for a description of treatments.

Catheters should be standardized and approved for use in both the US and EU. For each crossover portion, catheters should be inserted into the same ‘anatomical site’, preferably hand and forearm, with care taken to minimize cannula placement in the wrist or antecubital fossa.

Cannula insertion must be performed by a qualified health care professional. Aseptic technique must be used and standard precautions observed prior to and during vascular access placement. This includes the appropriate use of hand hygiene, glove selection, glove use, and decontamination of the peripheral catheter site with individually packaged alcohol wipes. Please note, only alcohol wipes are to be used to clean the site of catheter placement. Peripheral vascular access catheter placement will be documented for each volunteer in a separate source document. Information recorded will include batch number, gauge and length, number of attempts, anatomical location, and volunteer's response to placement. Care of the catheter site and restrictions are specified in advance. The mechanics of line clearance post infusion should be carefully considered.

For dosing in both study parts and for all infusions, the date and time of the infusion start and stop as well as the start and stop of any infusion interruption and restart of the infusion, and the actual volume and amount of ceftaroline fosamil infused will be recorded. In addition, the arm (left or right) in which the infusion is administered will be documented.

5.5.3 Additional study drug (not applicable)

5.5.4 Labelling

Labels will be prepared in accordance with Good Manufacturing Practice (GMP) and local regulatory guidelines. The labels will fulfill GMP Annex 13 requirements for labelling.

5.5.5 Storage

All IP should be kept in a secure place under appropriate storage conditions. The IP label specifies the appropriate storage.

Vials of ceftaroline fosamil for injection dry mixture should be stored at 2° to 8°C until ready for use. Vials should be used before the labeled expiry date.

5.6 Concomitant and poststudy treatment(s)

Apart from paracetamol/acetaminophen and hormone replacement therapy, no concomitant medication or therapy will be allowed. The volunteers should be instructed that no other medication is allowed including herbal remedies, vitamin supplements, and over-the-counter products without the consent of the Investigator.

Medication, which is considered necessary for the volunteer's safety and well-being, may be given at the discretion of the Investigator and recorded in the appropriate sections of the case report form (CRF). When any medication is required, it should be prescribed by the Investigator who should inform the CPA Physician. Following consultation with the CPA Physician, the Investigator should determine whether or not the volunteer should continue in the study.

5.7 Treatment compliance

The administration of all study drugs (including IP) should be recorded in the appropriate sections of the CRF.

Treatment compliance will be assured by supervised administration of the IP by the Investigator or delegate. The dose, dates, and times of administration of the IP will be recorded and will be checked by the monitor at monitoring visits.

5.7.1 Accountability

The study drug provided for this study will be used only as directed in the study protocol. The study centre personnel will account for all investigational products received at the study center, unused investigational product and for appropriate destruction. Certificates of delivery and destruction should be signed.

5.8 Discontinuation of investigational product and withdrawal from study

Volunteers may be discontinued from IP in the following situations:

- Volunteer decision. The volunteer is at any time free to discontinue treatment, without prejudice to further treatment.
- Adverse event
- Severe noncompliance to this CSP as judged by the Investigator and/or AstraZeneca
- Randomization in error (see Section 5.3)
- Catheter becomes dislodged or is removed from either arm prior to scheduled time point

Dosing for any individual volunteer will be stopped if the volunteer experiences a possibly drug-related SAE or a possibly drug-related significant nonserious AE, which in the opinion of the Investigator or Sponsor, warrants discontinuation from the study for that volunteer's well being.

Volunteers who have a VIP score of 2 or more will not have any further infusions in the affected arm for that treatment period. For Part A, if the infusion site in the contralateral arm is healthy, the infusions may continue in that arm.

Stopping criteria for Part A

Dosing will stop with an infusion volume (50, 100 or 250 mL) if any of the following scenarios occur with a reasonable possibility of a causal relationship with the investigational product:

- Two or more subjects report a serious adverse event (SAE) or have a VIP score of 5
- Four or more subjects have a VIP score of 4

During Part A of the study data will be reviewed by the Investigator on an ongoing basis. If 15 or more subjects develop ISRs, but the stopping criteria listed above have not been met, the Investigator may request an independent unblinded review of the available safety and tolerability data. If once unblinded the incidence of ISRs on any active volume is >40% of the total anticipated recruitment for Part A, an ad hoc data review meeting will be arranged between the Investigator, Sponsor, and other team members, as applicable, to determine study termination. Otherwise, dosing will be continued as planned in the remaining 50 mL subjects.

At completion of Treatment A (50 mL infusion volume), an unblinded review of the ISR incidence will be performed by a person who is not involved with the conduct of the study. If the cumulative ISR incidence is $\leq 40\%$ in both active treatments for the 50-mL and 250-mL infusion volume (Treatments A and C) as determined by the unblinded reviewer, the Investigator and Sponsor will be notified, and the study will proceed to Part B. However, if the cumulative ISR is >40% for the 50-mL active treatment (Treatment A) but is $\leq 40\%$ for the 250-mL active treatment (Treatment C), after review in the context of the corresponding placebo findings and following discussion with the Sponsor, Part A may be repeated with the 100-mL and 250-mL while Part B will be pending until after data review of the last cohort in Part A. In the instance of being repeated with 100 mL, the data review and study termination procedures in Part A will then be applied to the 100-mL treatment. At the completion of the last cohort for the 100-mL and 250-mL evaluation in Part A, if the cumulative ISR is $\leq 40\%$ in both active treatments for the 100-mL and 250-mL infusion volume (Treatments E and C) as determined by the un-blinded reviewer, the Investigator and Sponsor will be notified, and the study will proceed to Part B which will include Treatment E and Treatment C.

Procedures for discontinuation of a subject from investigational product

Volunteers are at any time free to withdraw from the study (IP and assessments), without prejudice to further treatment (withdrawal of consent). Such volunteers will always be asked about the reason(s) and the presence of any AEs. If possible, they will be seen and assessed by an Investigator. Adverse events will be followed up. See Sections [6.3.4](#) and [6.3.5](#).

Additional volunteers may be enrolled at the discretion of the Sponsor if the number of evaluable volunteers is not sufficient for either study part.

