- f A 12-lead ECG will be performed after the volunteer has rested in the supine position for 10 minutes prior to the evaluation.
- g The volunteer will fast for at least 4 hours prior to clinical laboratory evaluations.
- h Creatinine clearance will be estimated using the Cockcroft-Gault formula at screening and discharge.
- i A serum pregnancy test will be performed at screening and a urine pregnancy test at all other time points for all women of childbearing potential. If positive, the volunteer is excluded from participation in the study.
- j Performed as appropriate to confirm postmenopausal status.
- k Volunteers will be randomized in the morning of Day 1, Period 1, just prior to IP administration.
- l Crossover periods: The duration of dosing will start at the initial drug infusion and will continue every 12 hours until the volunteer has received multiple infusions up to 72 hours for a total of 6 infusions during each crossover period. Volunteers who experience a Visual Infusion Phlebitis score of 2 or more will not have any further infusions in the affected arm for the treatment period. The infusion in the contralateral arm may continue if the infusion site is healthy.
- m Vascular access site review of local tolerability will be performed by viewing in good lighting each of the infusion sites predose and at 20, 40, and 60 minutes, 6 hours, and 12 hours after the start of the infusion; the 12-hour assessment will be conducted prior to start of the second infusion. For the subsequent second to sixth infusions, local tolerability will be assessed at 20, 40, and 60 minutes, 6 hours, and 12 hours after the start of the infusion; the 12-hour assessment will be conducted prior to the start of the following infusion. Assessment will also occur as clinically indicated. A local reaction will be determined as an ISR and will be recorded as an AE when the severity score is 2 or more as measured by the Visual Infusion Phlebitis scale included in [Appendix D](#).
- n SAEs will be collected from the time when informed consent is signed until the follow-up visit. Non-serious AEs will be collected from Day -1 of Period 1 until the follow-up visit.

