6.3.1 Local tolerability measurements

Local tolerability will be assessed over time and graded using the VIP in [Appendix D](#). These assessments will occur as specified in Section [3.1.1](#). The VIP score will be recorded for all local reactions; any local reactions with a VIP score of 2 or greater will be determined an ISR and will be recorded as an AE.

The Investigator, or delegate, will assess the onset of ISR (eg, inflammation) by examining the catheter insertion site under good lighting conditions for the presence of erythema, tenderness, induration, swelling, drainage, or presence of palpable cord. Each infusion site will be assessed and either found to be unremarkable, ie, no evidence of ISR or presence of an ISR. When an ISR occurs the following information will be recorded on a separate source document: date and time, detailed description (including location, infusion volume, presence or absence of a palpable venous cord, and the extent [length and width] of inflamed tissue), and severity findings. The Investigator will record, report, and monitor the ISR as an AE when the severity score is 2 or more as measured by the VIP scale included in [Appendix D](#).

For those volunteers who experience an ISR, their washout period may be extended to allow recovery of the infusion site.

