1. INFUSION SITE REACTION ASSESSMENT

An infusion site reaction (ISR) is defined as an adverse event (AE) or laboratory abnormality possibly related to the peripheral cannula (eg, insertion, patency, maintenance) or the actual infusion of the study drug or placebo, judged by the Investigator or AstraZeneca. An ISR may commence at any time during the intravenous infusion administration. The most common examples of ISR that may be related to study drug and or vehicle include:

- Infiltration: The escape of nonvesicant solutions into the extravascular tissue causing local swelling and possible irritation
- Phlebitis: Inflammation of the vein and the surrounding tissue, caused by mechanical and/or chemical (study drug/vehicle) injury
- Thrombophlebitis: Inflammation of the vein and surrounding tissue caused by intravascular clot formation

Other nondrug-related cases of ISR should also be considered. **The clinical staff will assess the infusion site as described in CSP Section 6.3.1.** The Investigator will assess the onset of ISR (eg, inflammation) by examining the catheter insertion site under good lighting conditions for the presence of erythema, tenderness, induration, swelling, drainage, or presence of palpable cord. The Investigator will record and monitor the ISR as an AE and denote in the subject's clinic notes ISR, date and time, pertinent vitals, detailed description (including presence or absence of a palpable venous cord and the extent [length and width] of inflamed tissue), physical examination, laboratory (if indicated), severity findings, assessment, and plan. For all ISR AEs, severity should be assessed and reported utilizing the Visual Infusion Phlebitis (VIP) scale appended below.

Subsequent clinic notes should report progression (eg, scale score, if indicated) and date of resolution. Based on the Investigator's medical judgment, subjects experiencing an ISR related to inflammation at the catheter site should have the following considered:

- A digital photograph taken of the involved site (including a ruler in the field of view to allow the quantitation of the extent of inflammation)
- Peripheral Doppler Study: If thrombophlebitis is suspected
- Change of infusion insertion site (see below)

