2. MODIFIED VISUAL INFUSION PHLEBITIS SCALE

IV Site Appears Healthy	0	No signs of phlebitis OBSERVE CANNULA
One of the following is evident: 
 • Slight pain near IV site OR • Slight redness near IV site 	1	Possibly first signs of phlebitis OBSERVE CANNULA
Two of the following are evident: 
 • Pain at IV site • Erythema • Swelling 	2	Early stage of phlebitis Record as Adverse Event: Infusion Site Phlebitis Action: Discontinue further infusion/s and remove cannula in affected arm
ALL of the following signs are evident and extensive: 
 • Pain along path of cannula • Erythema • Induration 	3	Medium stage of phlebitis Record as Adverse Event: Infusion Site Phlebitis Action: Discontinue further infusion/s and remove cannula in affected arm. Consider treatment
ALL of the following signs are evident and extensive: 
 • Pain along path of cannula • Erythema • Induration • Palpable venous cord 	4	Advanced stage of phlebitis or the start of thrombophlebitis Record as Adverse Event: Infusion Site Phlebitis Action: Discontinue further infusion/s and remove cannula in affected arm. Consider treatment
ALL of the following signs are evident and extensive: 
 • Pain along path of cannula • Erythema • Induration • Palpable venous cord • Pyrexia 	5	Advanced stage of thrombophlebitis Record as Adverse Event: Infusion Site Thrombophlebitis Action: Discontinue further infusion/s and remove cannula in affected arm. Initiate treatment

IV intravenous.

Phlebitis scale, Jackson 1998. With permission from “Andrew Jackson, IV Nurse Consultant. The Rotherham NHS Foundation Trust, UK”

Clinical Study Protocol Appendix E

Drug Substance	Ceftaroline fosamil
Study Code	D3720C00015 (P903-30)
Edition Number	1
Date	

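### The second Part A stopping bullet counts VIP 4 rather than VIP 4 and above, so one VIP 5 plus three VIP 4 on a volume literally meets neither bullet

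*Supplement*

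**What the plan says.** Under Stopping criteria for Part A, Section 5.8 of the latest protocol in the Supplement gives two triggers. They apply separately to each infusion volume, and each requires a reasonable possibility of a causal link to the product.

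- The first trigger reads: "Two or more subjects report a serious adverse event (SAE) or have a VIP score of 5".
- The second trigger, which is the one at issue here, reads: "Four or more subjects have a VIP score of 4".

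Elsewhere the protocol uses open-ended wording for a threshold. For an affected arm, Section 5.8 itself says "Volunteers who have a VIP score of 2 or more will not have any further infusions", and Section 6.3.1 says "any local reactions with a VIP score of 2 or greater will be determined an ISR".

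In the Appendix D scale, grade 5 consists of the four grade 4 signs (pain along the cannula path, erythema, induration, palpable cord) with fever added; its list ends "Palpable venous cord • Pyrexia".

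Sites are scored at 20, 40 and 60 minutes, 6 hours and 12 hours after each infusion starts (Section 3.1.1). Section 6.3.1 has the score recorded for every local reaction.

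**The concern.** A severity-based stop should never become harder to trigger as outcomes get worse. Here the two bullets are separate counts of two exact grades, so moving one subject from grade 4 to grade 5 takes one from the second count without completing the first.

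The stop protects subjects not yet dosed at that volume. The 50 mL arm gives 12 mg/mL, while Section 3.2 puts the highest concentration previously infused in Phase 1 at 8 mg/mL. In one earlier healthy-volunteer study using 140 mL, 44% of those on active drug had injection-site events, all mild (Section 1.3). A mandatory stop at a new concentration should have only one possible reading.

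**Working it through.** The protocol states no operating characteristic for this stop, so there is no figure to reproduce.

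**Inputs.** The two bullets come from Section 5.8. Part A enrols 32 subjects to give at least 24 evaluable (Section 3.1.1), and each is due to receive each active volume once. For one volume, let a be the number of subjects counted at VIP 5 and b the number counted at VIP 4. Each subject is counted once, there are no SAEs, and every event is taken as possibly causal.

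- Literal rule: stop if a ≥ 2 or b ≥ 4.
- Reworded rule: stop if a ≥ 2 or a + b ≥ 4.

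**Step 1: where the rules differ.** If a ≥ 2, both stop. If a = 0, both reduce to b ≥ 4. If a = 1, the literal rule needs b ≥ 4 and the reworded rule needs b ≥ 3. The only difference is a = 1, b = 3, and there the reworded rule stops. Enumerating all counts up to 32 subjects confirms this, and no count moves the other way.

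| VIP 5 | VIP 4 | Literal | Reworded |
|---|---|---|---|
| 0 | 4 | stop | stop |
| 1 | 3 | no stop | stop |
| 1 | 4 | stop | stop |
| 2 | 0 | stop | stop |

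**Step 2: how likely that count is.** With assumed per-subject rates p5 and p4,

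P(1,3) = n × C(n−1, 3) × p5 × p4³ × (1 − p5 − p4)^(n−4).

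For n = 32 the leading factor is 32 × 4,495 = 143,840. At p5 = p4 = 5%: 143,840 × 0.05⁴ × 0.90²⁸ = 143,840 × 0.00000625 × 0.0523 = 0.047.

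| p5 (assumed) | p4 (assumed) | P(1,3), n = 32 |
|---|---|---|
| 1% | 2.5% | 0.8% |
| 2.5% | 2.5% | 1.3% |
| 1% | 5% | 3.2% |
| 5% | 5% | 4.7% |
| 5% | 10% | 7.6% |
| 3% | 10% | 8.7% |

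This probability is exactly what the rewording adds to the chance of stopping. For example, at p4 = 10% and p5 = 3% the chance goes from 0.558 to 0.645. With n = 24 the gain runs from 1.5% (p4 = 5%, p5 = 1%) to 8.2% (p4 = 10%, p5 = 5%).

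**Step 3: direction.** Fix the combined rate of VIP 4 or 5 at an assumed 12% with n = 32, and raise the share that is VIP 5 from 0% to 15%. The literal stop probability falls from 0.546 to 0.485. Under the reworded rule it rises from 0.546 to 0.562. At larger shares the literal figure recovers (0.637 at 50%) because the two-subject trigger takes over.

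**Step 4: who falls into the gap.** A subject who reaches 5 with no recorded 4 cannot count towards the second bullet as worded. A subject scored 4 and later 5 has a recorded 4. That subject drops out of the second count only if each subject is represented by worst or current score, and the protocol does not say which convention applies.

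**The case against.** The scale is nested: any VIP 5 site shows all four VIP 4 signs, so a sensible reader would count it towards the four. Scores are also recorded serially, so most worsening subjects would have a VIP 4 on record. This probably reflects what was intended, and it is why the change is a small one. It does not alter the wording, which counts a score rather than a set of signs and departs from the protocol's own at-or-above phrasing.

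Other safeguards limit harm. The affected arm stops at VIP 2 or more, the Investigator reviews data continuously, an unblinded review may be requested at 15 subjects with reactions, and the sponsor can terminate for safety (Section 9.5). These stand, but none is an automatic stop for this count.

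A reader might infer that worsening from 4 to 5 always prevents a stop, or undoes one. The documents do not support that. The first depends on the missing counting convention, and a stop already triggered by four VIP 4 subjects is not reversed.

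A reader might also infer that VIP 5 cannot be recognised because temperature is not a scheduled measurement. Scheduled vital signs are indeed blood pressure and pulse (Section 6.3.9), and the site signs in Section 6.3.1 are local: "for the presence of erythema, tenderness, induration, swelling, drainage, or presence of palpable cord". But for each reaction Appendix D directs the Investigator to enter "clinic notes ISR, date and time, pertinent vitals, detailed description" and a physical examination, and to grade by the VIP scale. Grade 4 and grade 5 cannot be told apart without judging fever. Table 2, footnote m, adds "Assessment will also occur as clinically indicated". What is missing is a named reading and a cutoff, which is operational detail. A large effect appears only at an extreme: with an assumed 5% VIP 5, no VIP 4 and no fever ever recognised, the stop probability at n = 32 falls from 0.48 to 0.07. That is a bound, not an expectation.

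**Conclusion.** The wording gap is real and minor. Literally read, one VIP 5 plus three VIP 4 on a volume does not trigger the mandatory stop that four VIP 4 would, provided no further subject on that volume has a related SAE. It affects that single count and nothing else. It is certain for a VIP 5 subject without a recorded 4, and conditional on the counting convention for one who passed through 4.

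The chance of reaching the gap, about 1% to 9% at n = 32 across the pairs shown, rests wholly on assumed rates. These may be high: earlier healthy-volunteer events were mild, and monkeys infused at up to 80 mg/mL showed no major irritation (Sections 1.3 and 3.2). The incidence of infusion site reactions and the 40% rule are unaffected, because both count VIP 2 and above.

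**What to change.** In Section 5.8, extend the second bullet to read "Four or more subjects have a VIP score of 4" *or greater*. This moves one count from no stop to stop and none the other way. It also settles the counting question, because a subject at 5 then counts towards the four whether or not a 4 was recorded.

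Optionally, name body temperature among the vitals that Appendix D asks for when a site scores VIP 2 or more, and state the value that counts as pyrexia. Temperature at every scoring time is not needed.

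The cost is two words in an amendment. The optional part adds a thermometer reading at assessments of a reacting site and a place to record it. Neither change adds visits, staff or subjects.
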